9.6. Data Management

The study will use an electronic data entry system (eCRF), all users will receive specific access codes to enable them to enter their data. The electronic data entry system will contain automatic checks for data completeness and inconsistent data.

9.7. Data Analysis

• Descriptive analysis:

Categorical and ordinal variables will be described by sample size and the frequency of each modality (over the total number of responses).

Quantitative variables will be described by the number of responses, mean, standard deviation, minimum, maximum, median of all available data.

• Inferential analysis:

When deemed necessary, sub-group comparisons and/or between time point comparisons may be implemented.

Patients who are lost to follow-up or discontinue therapy for any reason, including leaving the study for non-medical reasons will be censored at the discontinuation date. Person time will be computed from baseline to discontinuation and used as such for any time to event analysis.

• Multivariate analysis

The potential dependence of treatment outcome frequency with other variables or baseline characteristics will be investigated through multivariate analysis.

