ALT < ULN* HBeAg-loss	71%	77 %		
HBeAg-seroconversion HBsAg-loss**(HBeAg+ at baseline)	19 % 5.1 %			
HBsAg-loss (HBeAg- at baseline) $2/226$ with documented HBsAg*ULN: Male ≤ 43 IU/L, female ≤ 34 IU/L; ** Kaplan Meier Estimate (Cumulative probability in patients with documented HBsAg)				

Table 2: 2 years virological, serological and biochemical results[28]

Tuble of of cume clearance aaring fonon ap	Table 3:	Creatine-clearance	during	follow-up
--	----------	---------------------------	--------	-----------

Estimated CrCl (Cockcroft-Gault)	Baseline (n = 361)	Month 6 (n = 299)	Month 12 (n = 289)	Month 24 (n = 255)
Mean [ml/min] (SD)	106.9 (31.6)	105.9 (33.8)	104.7 (31.7)	102.2 (31.3)
Mean change [ml/min] (SD)		-1.4 (16.1)	-3.2 (16.2)	-3.4 (15.4)

8. **RESEARCH QUESTION AND OBJECTIVES**

Clinical studies, such as RCT's investigate the efficacy and safety of a drug in predefined populations, therefore providing high internal validity. Data generated in real-life settings allows for investigating the external validity of the effects seen in RCTs. Thus the real-life treatment outcomes of the drug can be investigated in observational studies such as non-interventional studies (NIS).

The real-life treatment outcomes of Viread[®] have been investigated in GEMINIS for a period of 3 years. VIR-Life is the roll-over non-interventional study from GEMINIS to allow for the continued prospective evaluation of the real-life treatment outcomes for additional 3 years.

The primary objective of this study is as follows:

• Prospectively describe the virological response, defined as HBV-DNA concentration, during 6 years Viread[®] treatment for CHB in a real life setting.

The secondary objectives of this study are to evaluate the:

- To describe the safety and tolerability of 6 years of Viread[®] in CHB in a real life setting, and report the following:
 - Adverse drug reactions (ADR) (unrelated Adverse Events (AEs) will also be listed in the report)
 - Renal safety
 - Estimated creatinine clearance (eCrCl)
 - Serum creatinine level
 - Serum phosphorus level
- Histological improvement of the liver

9. **RESEARCH METHODS**

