9.2. Setting / Study Population

VIR-Life is a roll-over study in adult, HBV-mono-infected CHB patients who started CHB treatment with Viread[®] in GEMINIS. Patients in GEMINIS, and therefore now in VIR-Life, are collected nationwide in a real-life setting at approximately 25 of the initial 35 GEMINIS sites. The study sites are either office based physicians with hepatological focus or hospitals with dedicated hepatological outpatient care units.

If the physician decided to treat and document a patient monoinfected with HBV with Viread[®] in GEMINIS and later in VIR-Life, he/she can document the course of the therapy (at months 48, 60 and 72) within the scope of a non-interventional study (NIS).

Eligibility criteria:

Patients completing 3 years in GEMINIS and still receiving a Viread[®]-containing regimen may roll over into this study

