9.2.2. Rationale for the patient number

The target number of 250 patients, followed up at approximately 25 well distributed study sites, supports representativeness of the drawn sample to the overall CHB-population currently treated with Viread[®] in Germany. It is expected that the patient number of 250 supports conclusions on the treatment results in major subpopulations (e.g., elderly patients). The 6 year long term follow up data from 250 patients is expected to contribute to the safety profile of Viread in CHB patients in a real life setting.

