9.4.1. Baseline

VIR-life is the extended follow up of GEMINIS. Therefore, VIR-life baseline data is the data that was collected at GEMINS baseline.

9.4.2. During VIR-Life follow up and at end of follow up (month 48, 60 and 72):

- HBV- virology and serology parameters
- Biochemical serum-parameters
 - ALT
- Renal safety parameters
 - Serum creatinine, eCrCl, serum phosphorus
- Liver synthesis parameters
 - Albumin, bilirubin, thrombocytes, prothrombin time (Quick-Value)
- Liver histology, elastography, incident HCC
- Co-morbidities, Co-infections, alcohol consumption
- Adverse events
- Special Situations; pregnancies, medication error, abuse, misuse, overdose, lack of effect, adverse events in infants following breastfeeding, and adverse events associated with product complaints
- Dosing of Viread[®]
- Combination therapy
- Reason for discontinuation of Viread[®], if applicable

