9.9. Limitations of the research methods

In a non-interventional study all decisions on the management of the patient are made solely by the treating physician. This also includes the frequency of the evaluation of lab values and other collected variables. Documentation of study variables must not be made obligatory. Missing data of unpredictable extent can occur.

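### Virological results are summarised over documented values in patients selected for three completed years still on Viread, so they are likely to overstate six-year response and do not support the representativeness claim

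*Protocol*

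**What the plan says.** The primary objective (Section 8) is to "Prospectively describe the virological response, defined as HBV-DNA concentration, during 6 years" of Viread treatment. Baseline is set at the start of GEMINIS (Section 9.4.1): "VIR-life baseline data is the data that was collected at GEMINS baseline".

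Entry is at month 36 and is conditional (Section 9.2): "Patients completing 3 years in GEMINIS and still receiving a Viread[®]-containing regimen may roll over into this study". About 25 of the 35 GEMINIS sites are invited (Sections 9.2 and 9.2.1), and 250 of the 400 GEMINIS patients are expected (Section 9.5).

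Section 9.7 gives two summary rules. For categorical variables: "Categorical and ordinal variables will be described by sample size and the frequency of each modality (over the total number of responses". For quantitative variables: "Quantitative variables will be described by the number of responses, mean, standard deviation, minimum, maximum, median of all available data". Section 9.9 says that documentation cannot be made obligatory and that "Missing data of unpredictable extent can occur".

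Section 9.2.2 states that 250 patients at about 25 sites "supports representativeness of the drawn sample to the overall CHB-population currently treated with Viread" in Germany.

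**The concern.** Two filters lie between the patients who started Viread and the reported result. The first is entry: anyone who stopped Viread or left GEMINIS before month 36 is outside VIR-Life. The second is documentation: an enrolee without a value in a visit window drops out of that visit's summary, whether HBV-DNA is shown as a category or as a concentration.

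Both filters plausibly favour responders, since patients who do poorly have more reason to stop, switch or leave. Yet the objective and the choice of baseline present the result as six years of treatment from the start, and 9.2.2 extends it to all current users. A reader of the final report could take a high month-72 figure as the outlook for a patient starting Viread, when it describes patients already known to have stayed on it for three years and to have been tested.

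**Working it through.** **No planned figure to reproduce.** The 250 is set by availability (Sections 9.5 and 9.10), without a power or precision target. It is 250/400 = 62.5% of the GEMINIS cohort.

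**Bounding the documentation filter.** Let p be the response rate among documented enrolees, r the share documented and q the unknown rate among the undocumented.

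- Rate over all enrolees = p·r + q·(1 − r)
- Documented rate minus that rate = (1 − r)·(p − q)

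*Input p.* Taken from the month-24 GEMINIS rates below 169 IU/ml (Table 2), assuming 69% HBeAg-negative in both groups.

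- Treatment-naïve: 0.31 × 88 + 0.69 × 94 = 92.1%
- Experienced: 0.31 × 94 + 0.69 × 97 = 96.1%
- Weighted 183:217: (183 × 92.1 + 217 × 96.1)/400 = 94%

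The same sum for the 69 IU/ml threshold gives about 85%.

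*Input r.* The protocol gives no expected HBV-DNA documentation rate, so 60% to 90% is assumed.

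| p | r | q = 0 | q = 70% | q = p | q = 100% |
|---|---|---|---|---|---|
| 94% | 60% | 56.4% | 84.4% | 94.0% | 96.4% |
| 94% | 90% | 84.6% | 91.6% | 94.0% | 94.6% |
| 85% | 60% | 51.0% | 79.0% | 85.0% | 91.0% |
| 85% | 90% | 76.5% | 83.5% | 85.0% | 86.5% |

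For example, with p = 94% and r = 60%: 0.94 × 0.60 = 56.4% at q = 0, and 56.4% + 40% = 96.4% at q = 100%. The plan would report 94% in every one of the first two rows.

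**Is 60% too pessimistic?** The only documentation counts in the protocol are for creatinine clearance (Table 3): 361, 299, 289 and 255 patients at baseline and months 6, 12 and 24. Carrying the whole 24-month rate over 36 months gives (255/361)^1.5 = 0.59, or about 148 of 250. But loss was front-loaded. The month 12 to 24 rate gives (255/289)^3 = 0.69, or about 172 of 250. These counts are a proxy for HBV-DNA documentation, so they show only that the assumed range is not fanciful.

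**The entry filter and the site filter.** 400 − 250 = 150 GEMINIS patients lie outside the planned cohort. Some are absent only because their site was not invited: about 400 × 10/35 = 114 if sites were of equal size, or at most 10 × 4 = 40 if the ten sites each enrolled fewer than five. The protocol does not allow the 150 to be split between site non-participation and treatment outcome.

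**Representativeness.** GEMINIS enrolled from May 2009 to May 2010 and VIR-Life entry requires three completed years. Patients who started Viread more recently are among those currently treated, but none can be in the sample.

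**The case against.** The roll-over design is stated openly, and the protocol takes real steps against selection. All eligible patients at participating sites are to be rolled over, with reasons recorded for those who are not (Section 9.2.3). Patients who stop Viread remain under documentation to month 72 (Section 9.3). Section 9.7 requires the sample size beside each frequency, so the denominator is visible. The 9.2.2 claim concerns patients currently treated, so leaving out those who stopped partly fits that target. Imputation, weighting and repeated-measures models usually belong in an SAP, which is not shown.

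Much of this stands, and the point does not rest on a missing method. It rests on what the protocol fixes: the summary rules, the entry condition and the representativeness statement. The log in 9.2.3 covers eligible patients only, so it does not reach those lost before month 36. Follow-up after stopping is put in doubt by 9.7, which censors patients at discontinuation.

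Several stronger readings are tempting but unsupported:

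- *Response will certainly be overstated.* The bounds reach above the documented rate. Some undocumented patients may be stable and tested less often, or may have stopped after a good outcome.
- *Treatment failures are excluded.* Section 9.2 has no virological criterion, so a viraemic patient still on a Viread-containing regimen may enter.
- *Table 3 shows that missingness was not neutral.* Assuming every patient with a follow-up value also had a baseline value, those without a month-24 value had an implied baseline clearance of (361 × 106.9 − 255 × 105.6)/106 = 110.0 ml/min, against 105.6. The gap is about 1.2 standard errors (4.4/3.65, using SD 31.6). It reverses at month 6 (105.0 against 107.3) and month 12 (102.9 against 107.9), and it concerns renal function, not virology.
- *All 400 starters with missing counted as failure give a fair lower bound.* That would score patients at uninvited sites as non-responders.

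**Conclusion.** The point holds in a limited form. As planned, the virological results describe patients who stayed on Viread for three years and were then documented. Upward bias relative to response from treatment start is the likely direction, but the protocol gives no rate for undocumented patients, so neither size nor sign can be fixed. Under the assumptions above (94% suppressed among documented patients, 60% to 90% of 250 documented), the rate over all enrolees lies between 56% and 96% at the low end of documentation and between 85% and 95% at the high end. These are bounds, not estimates, and they cover the documentation filter alone. The effect of selection before month 36 comes on top and cannot be quantified from the protocol.

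The representativeness claim in 9.2.2 fails whatever the direction of bias, and 9.9 names missing data but not this selection. The study remains useful as a description. Its wording claims more than its design supports, and this should be corrected.

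**What to change.** 1. In 9.7, report the month-48, 60 and 72 virological result over documented patients and over all VIR-Life enrolees, with missing counted as non-response and labelled a lower bound. This needs a stated HBV-DNA threshold; GEMINIS reported 169 and 69 IU/ml. Beside concentration summaries, give the number of enrolees without a value.
2. Compare GEMINIS baseline characteristics of rolled-over and non-rolled-over patients, separating those whose site did not take part from those who stopped Viread or left before month 36.
3. Reword the objective and 9.2.2 to *patients who completed three years in GEMINIS and remained on Viread*, and name this selection as a limitation in 9.9.
4. Reconcile 9.3 and 9.7 on whether values after discontinuation of Viread count.

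An inverse-probability-weighted analysis is optional. It should not be planned on the premise that month-36 data are held for every patient, which the protocol does not show.

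The cost is a few table columns, one baseline comparison and some rewording, with no new visits. The downside is a less favourable figure beside the headline, which must be clearly marked as a bound.

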	 Weight Serum HBV-DNA concentration HBeAg, anti-HBe; HBsAg, antiHBs ALT-level Serum creatinine, eCrCL, serum phosphorus Albumine, Bilirubine, Thrombocytes, Prothrombine time (i.e. Quick value) Liver histology staging, transient elastography HCC development Co-morbidities, Incident co-infections with HIV, HCV or HDV Amount of alcohol consumption Adverse events Special Situations; pregnancies, medication error, abuse, misuse, overdose, lack of effect, adverse events in infants following exposure from breastfeeding and adverse events associated with product complaints Dosing of Viread[®] Reason for discontinuation of Viread[®], if applicable 		
Data Sources:	Collection of routine visit data via eCRF		
Study Size:	250 patients		
Data Analysis:	 Descriptive analysis: Categorical and ordinal variables will be described by sample size and the frequency of each modality (over the total number of responses). Quantitative variables will be described by the number of responses, mean, standard deviation, minimum, maximum & madian of all available data. 		

	• Inferential analysis:
	When deemed necessary, sub-group comparisons and/or between time point comparisons may be implemented.
	• Multivariate analysis:
	The potential dependence of treatment outcome frequency with other outcome variables or baseline characteristics will be investigated through methods of multivariate analysis.
Milestones:	Start of data collection : approx. May 2013
	End of Data collection: December 2016
	Interim analysis: planned for Sept. 2014 (year 4 data) and Sept. 2015 (year 5 data)
	Final Study report: April 2017 (year 6 data)
	Publication: submission in Q2-3 2017

This study will be conducted in accordance with the guidelines of Good Pharmacoepidemiology Practices (GPPs), Heads of Medicines Agencies (HMA) and Good Pharmacovigilance Practices (GVP) including archiving of essential documents.

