9.3. Variables

In this non-interventional post-authorization safety study the time the subject has taken Viread[®] is the exposure of interest. Outcome variables are the collected clinical and laboratory parameters, i.e.:

Primary outcome variable:

- Virology
 - Serum HBV-DNA

Secondary outcome parameters are:

- Serology
 - HBeAg/anti-HBe (qualitative)
 - HBsAg/anti-HBs (qualitative)
- Biochemistry parameter
 - o ALT
- Renal function parameters

- Serum creatinine
- Creatinine Clearance (estimated via Cockcroft-Gault, MDRD or CKD Epi formula)
- Serum phosphorus
- Liver synthesis parameters
 - o Albumin
 - o Bilirubin
 - Thrombocytes
 - Prothrombin time [i.e. Quick-Value]
- Safety parameters
 - Adverse events
 - Special Situations; pregnancies, medication error, abuse, misuse, overdose, lack of effect, adverse events in infants following exposure from breastfeeding and adverse events associated with product complaints
- Incident cases of co-infections
 - o HIV
 - o HCV
 - o HDV
- Co-morbidities (incident and prevalent cases)
 - o Ascites
 - o Jaundice
 - Diabetes mellitus
 - Lipometabolic disorders
 - o Coronary heart disease
 - Hypertension

- Alcohol consumption per week
- Liver histology and HCC
 - Liver biopsy results
 - o Fibroscan
 - o HCC
- Dosing and dose alterations
- Combination therapy
- Treatment discontinuations
 - Patients discontinuing Viread should not be discontinued from study follow up. All study variables in these patients shall be documented in VIR-life until month 72

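### The descriptive rule in 9.7 sets no on-treatment limit, so HBV-DNA values recorded after stopping Viread can enter summaries meant to describe response during Viread treatment

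*Protocol*

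**What the plan says.** Section 8 of the protocol gives the primary objective: "Prospectively describe the virological response, defined as HBV-DNA concentration, during 6 years Viread[®] treatment for CHB in a real life setting". Section 9.3 states that "the time the subject has taken Viread[®] is the exposure of interest".

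Section 9.3 also says what happens when a patient stops: "Patients discontinuing Viread should not be discontinued from study follow up", and "All study variables in these patients shall be documented in VIR-life until month 72". Serum HBV-DNA is the primary outcome variable in that same section, so it is among the variables collected after stopping.

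For the descriptive analysis, Section 9.7 summarises quantitative variables by "mean, standard deviation, minimum, maximum, median of all available data" and categorical variables by "the frequency of each modality (over the total number of responses" received). The synopsis repeats the quantitative rule: "mean, standard deviation, minimum, maximum & madian of all available data". None of these statements is limited to values on Viread.

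Under inferential analysis, Section 9.7 censors patients who are lost to follow-up or stop therapy at the date of discontinuation. The next sentence reads: "Person time will be computed from baseline to discontinuation and used as such for any time to event analysis".

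Under Section 9.2, patients must still be on a Viread-containing regimen when they roll over after three years. Section 9.4.2 collects dosing and the reason for discontinuing Viread.

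**The concern.** The objective concerns patients while they take Viread. The data collection deliberately extends past stopping, and the summary rule takes whatever has been collected. Applied literally, these three statements produce a month-72 HBV-DNA result that would be read as response on Viread but would include patients no longer taking it.

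Everyone is on Viread at roll-over, so the mixing can arise only at the visits that VIR-Life adds (months 48, 60 and 72). Those visits are the new information in the six-year result.

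**Working it through.** **Reading the sections together**

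1. Objective (Section 8): response during Viread treatment, which points to on-treatment values.
2. Collection (Section 9.3): HBV-DNA to month 72 whether or not Viread continues.
3. Descriptive rule (Section 9.7 and synopsis): all observed values, no limit by treatment status.
4. Censoring rule (Section 9.7): stated under inferential analysis and followed directly by a person-time rule for time-to-event work. The primary objective is to describe, so it falls under the descriptive rule, which the censoring sentence does not clearly reach.

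**Size for the proportion suppressed**

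The protocol states no figure that can be reproduced here. What follows is illustration.

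- N = 250 (Section 9.5), taking every patient to have a value at the visit.
- Proportion suppressed on Viread, p_on = 90%, assumed. The month-24 GEMINIS values in Table 2 run from 80% to 100%.
- Share of values taken after stopping, f = 5% or 10% (12.5 or 25 of 250), assumed.
- Proportion of stoppers suppressed, p_off = 95%, 70% or 50%, assumed.

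Shift (pooled minus on-Viread) = f × (p_off − p_on):

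| p_off | f = 5% | f = 10% |
|---|---|---|
| 95% | 0.05 × 5 = +0.25 points | 0.10 × 5 = +0.5 points |
| 70% | 0.05 × (−20) = −1.0 points | 0.10 × (−20) = −2.0 points |
| 50% | 0.05 × (−40) = −2.0 points | 0.10 × (−40) = −4.0 points |

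For scale, the 95% sampling margin is 1.96 × √(0.90 × 0.10 / 250) = 3.7 points. The shift exceeds the margin only when p_off is below p_on − margin/f:

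- f = 10%: 0.90 − 0.0372/0.10 = 53%.
- f = 5%: 0.90 − 0.0372/0.05 = 16%.

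With p_on = 97% (Table 2, treatment-experienced HBeAg-negative patients, below 169 IU/ml), the margin is 1.96 × √(0.97 × 0.03 / 250) = 2.1 points. The two break-evens become 76% and 55%.

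**Size for the arithmetic mean**

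Section 8 defines response as HBV-DNA concentration, and Section 9.7 includes the mean. Assume 20 IU/ml on Viread and 100,000 IU/ml after stopping. With 5% stopped, the pooled mean is 0.95 × 20 + 0.05 × 100,000 = 5,019 IU/ml. A single stopper among 250 who returned to the baseline upper quartile in Table 1 (4.0 × 10⁵ IU/ml) would add about 400,000/250 = 1,600 IU/ml. The GEMINIS thresholds are 69 and 169 IU/ml. The median would barely move.

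**Renal check**

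Take the month-24 mean change in estimated creatinine clearance as the on-Viread value: −3.4 ml/min, SD 15.4 (Table 3). Shift = f × (d_off + 3.4), where d_off is the stoppers' mean change:

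- d_off = −5: −0.08 (f = 5%) or −0.16 (f = 10%) ml/min.
- d_off = 0: +0.17 (f = 5%) or +0.34 (f = 10%) ml/min.

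The standard error is 15.4/√250 = 0.97 ml/min, so these shifts are small.

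**The case against.** Section 9.7 is a short generic list, and choosing analysis sets or flagging visits against a stop date is ordinary content for a statistical analysis plan, which is not at hand. That is fair as far as detail goes. The protocol does, however, name the data to be summarised and requires post-stop data to be collected. Together these miss its own objective, so the point is more than missing detail.

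The phrase about available data may mean only observed values without imputation, and Section 9.9 does warn of missing data. That reading is natural, but an observed post-stop value is still an available value, so it would still be included.

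The censoring sentence covers patients who stop therapy for any reason and is not itself restricted to time-to-event analysis. This stands in part: a reader could extend it to the descriptive tables, so pooling is the literal reading and not a settled fact. A reader might also infer that 9.7 contradicts itself. The documents do not support that, because the two rules stand under different types of analysis.

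An all-follow-up summary is a legitimate real-life estimate, and an on-Viread summary is selected for persistence. This stands, and it is why both should be shown.

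The study is descriptive, with no test or decision rule. Either summary can be produced at analysis, so nothing is irretrievably lost. This also stands and limits the severity.

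**Conclusion.** The point holds as a mismatch between the stated objective and the literal descriptive rule for HBV-DNA at months 48, 60 and 72. It is a cheap improvement of minor severity.

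Its size cannot be derived from the protocol, because stopping and suppression rates after stopping are both assumed. The effect on the proportion suppressed is near zero if few stop or if stoppers stay suppressed, for example on another drug. It is a few percentage points if about 10% stop and half or more of them are viraemic. The arithmetic mean of HBV-DNA is more exposed than the proportion or the median.

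A reader might infer that the primary result will be materially biased, or that renal conclusions would change. The documents support neither: they give no rates from which to establish a material bias, and the illustrated renal shifts are below 0.5 ml/min. For the renal tables the matter is one of labelling only.

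**What to change.** In Section 9.7, classify each month-48, 60 and 72 HBV-DNA value as on Viread or after stopping, using the stop date. Report the on-Viread result against the primary objective and the all-follow-up result beside it. The synopsis should carry the same wording. The renal tables may use the same flag for labelling. As a clarification only, one clause could say whether censoring at the end of therapy is confined to time-to-event analyses.

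The cost is about two sentences in Section 9.7 and one extra column in the HBV-DNA tables. No new data are needed: the censoring rule already requires the discontinuation date, and Section 9.4.2 already collects dosing and the reason for stopping. The downside is that the on-Viread set is smaller and selected for persistence; the all-follow-up column keeps that visible.

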Laboratory abnormalities without clinical significance are not recorded as AEs or SAEs. However, laboratory abnormalities (eg, clinical chemistry, hematology, and urinalysis) that require medical or surgical intervention or lead to drug interruption, modification, or discontinuation must be recorded as an AE, as well as an SAE, if applicable. In addition, laboratory or other abnormal assessments (eg, electrocardiogram, x-rays, vital signs) that are associated with signs and/or symptoms must be recorded as an AE or SAE if they meet the definition of an AE or SAE as described in Section 10.1. If the laboratory abnormality is part of a syndrome, record the syndrome or diagnosis (eg, anemia), not the laboratory result (ie, decreased hemoglobin).

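### Section 9.7 censors at Viread discontinuation in every time-to-event analysis, although Section 9.3 keeps these patients under observation to month 72

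*Protocol*

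**What the plan says.** Protocol Section 9.7 (Data Analysis), under inferential analysis, covers patients who are lost to follow-up and patients who "discontinue therapy for any reason, including leaving the study for non-medical reasons will be censored at the discontinuation date". It continues: "Person time will be computed from baseline to discontinuation and used as such for any time to event analysis". No lag, exception or accompanying analysis is named.

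Section 9.3 (Variables, treatment discontinuations) says: "Patients discontinuing Viread should not be discontinued from study follow up". It adds: "All study variables in these patients shall be documented in VIR-life until month 72".

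Four other places bear on the point:

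- Section 9.4.2 lists "Reason for discontinuation of Viread" among the items collected at months 48, 60 and 72.
- Section 11.1.3 says that laboratory abnormalities that "lead to drug interruption, modification, or discontinuation must be recorded as an AE".
- Section 9.3 names "the time the subject has taken Viread" as the exposure of interest.
- Section 9.7 describes quantitative variables by the number of responses and the "mean, standard deviation, minimum, maximum, median of all available data".

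**The concern.** Loss to follow-up ends observation. Stopping Viread does not, because Section 9.3 requires sites to go on documenting. Section 9.7 nevertheless gives both the same censoring date. Two consequences follow.

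First, an event after the stop, such as HCC, HBsAg loss or a later renal event, enters no time-to-event estimate, even if it occurs shortly after the last dose and has been recorded.

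Second, censoring is harmless only if patients who stop have, at that moment, the same event risk as those who continue. The protocol gives a reason to doubt this. It foresees laboratory abnormalities that lead to discontinuation (Section 11.1.3), and renal safety is a secondary objective (Section 8). It collects the reason for stopping, but the censoring rule makes no use of it.

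VIR-Life is described as a post-authorization safety study (Section 9.1), so what is at stake is the completeness of its event risks over six years.

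**Working it through.** **No plan figure to reproduce.** The size of 250 is set by the patients available for roll-over (Section 9.5). Discontinuation rates and event rates are not given.

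**Step 1: the passages side by side.**

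| Situation | Observation (Section 9.3) | Time-to-event analysis (Section 9.7) |
|---|---|---|
| Lost to follow-up | ends | censored |
| Stops Viread, stays in study | continues to month 72 | censored at the stop |

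The second row is the conflict. The rule covers any time-to-event analysis, so an analysis plan that used the later follow-up would depart from the protocol.

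**Step 2: person-time left out.** From the documents: N = 250 and T = 3 years (months 36 to 72). Assumed: a proportion d stops over the three years at a constant rate λ = −ln(1 − d)/3, with no true loss to follow-up. Full follow-up gives 250 × 3 = 750 person-years. The rule keeps 250 × d/λ.

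- d = 5%: λ = 0.01710; 12.5/0.01710 = 731.1 kept, 18.9 lost (2.5%).
- d = 10%: 711.8 kept, 38.2 lost (5.1%).
- d = 20%: 672.2 kept, 77.8 lost (10.4%).
- d = 30%: λ = 0.11889; 75/0.11889 = 630.8 kept, 119.2 lost (15.9%).

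Baseline is the GEMINIS baseline (Section 9.4.1), so against all six years (250 × 6 = 1,500 person-years) these shares halve: 18.9/1,500 = 1.3% to 119.2/1,500 = 7.9%.

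**Step 3: possible bias from informative censoring.** All rates are assumed. A hidden 20% of patients have k times the event hazard and k times the stopping hazard of the rest. Stopping itself does not change a patient's hazard. For the other 80%, let a be the event hazard and b the stopping hazard per year.

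- Set a so that the true 3-year risk is 10%: 0.8·exp(−3a) + 0.2·exp(−3ka) = 0.90. This gives a = 0.03512 for k = 1, 0.02552 for k = 3 and 0.01376 for k = 10.
- Set b so that a proportion d stops: 0.8·exp(−3b) + 0.2·exp(−3kb) = 1 − d.
- The hazard seen in the censored risk set is h(t) = [0.8·a·exp(−(a+b)t) + 0.2·k·a·exp(−k(a+b)t)] / [0.8·exp(−(a+b)t) + 0.2·exp(−k(a+b)t)].
- The large-sample Kaplan-Meier value is 1 − exp(−∫h(t)dt) over 0 to 3 years.

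| Stopping over 3 years | k = 1 | k = 3 | k = 10 |
|---|---|---|---|
| 5% | 10.0% | 9.9% | 9.6% |
| 10% | 10.0% | 9.8% | 9.2% |
| 20% | 10.0% | 9.7% | 8.3% |
| 30% | 10.0% | 9.5% | 7.4% |

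In the worst cell (k = 10, d = 30%, b = 0.06043), the high-risk share of the risk set falls from 20% to 3.3%. The observed hazard falls from 3.85% to 1.78% per year, although no patient's own hazard has changed.

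**The case against.** The strongest reply is that on-treatment person time is what this study wants. Time on Viread is the stated exposure, the objectives speak of six years of Viread, and only patients still on a Viread-containing regimen may roll over. An analysis to month 72 mixes time off drug into a single-arm estimate. This stands: the rule is legitimate as one labelled analysis, and making the month-72 analysis primary is a debatable choice. But a stated exposure does not make the censoring non-informative, and it does not explain why follow-up after stopping is ordered and then given no place in any time-to-event estimate.

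The reply also limits the reach of the point in three ways, and all three stand. No objective or outcome is defined as time to event, and Section 9.7 leaves inferential comparisons optional; the nearest precedent is the parent study's Kaplan-Meier estimate of HBsAg loss (Section 7.3, Table 2). Post-stop laboratory values stay in the descriptive summaries, which serve the primary HBV-DNA objective. An abnormality that prompts stopping will normally precede the stop and be counted, so only later events are lost.

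A reader might infer a larger effect by letting the hazard rise after stopping. With assumed hazards of 1% per year on drug and 5% after, and 5% per year stopping, the rule gives 1 − exp(−0.03) = 2.96%. Full follow-up gives 1 − [exp(−0.18) + 0.05·exp(−0.15)·(1 − exp(−0.03))/0.01] = 3.75%. The arithmetic is right, but in that model stopping is unrelated to risk on drug, so 2.96% is the correct on-treatment risk. The gap is a difference between two target quantities and is not evidence of informative-censoring bias.

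**Conclusion.** The conflict between Sections 9.3 and 9.7 is in the current text and holds. Events after stopping are left out of every time-to-event estimate, and the censoring can be informative where stopping is related to outcome. Whether it is, and by how much, cannot be found from the documents.

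Under the assumed model the bias is nil without a link, at most 0.5 percentage points on a 10.0% risk with a threefold link, and up to 2.6 points with a tenfold link and 30% stopping. The model assumes that patients at higher risk stop more often; the opposite link would push the estimate upward.

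A reader might conclude that late safety outcomes are understated, or that the data collected after stopping are thrown away. The documents support neither as a flat statement. The first is conditional on the link, and the second is true of time-to-event analyses only. The primary objective is not threatened. This is an inexpensive improvement to a safety study.

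**What to change.** In Section 9.7:

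- Separate loss to follow-up from drug discontinuation.
- Keep the present rule, labelled as an on-treatment analysis.
- Report beside it, for safety and clinical events, an analysis that follows every patient to the event, last documented contact, death or month 72, regardless of Viread discontinuation.
- Tabulate discontinuations by the reason already collected.

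Which analysis is primary, the length of any lag after the last dose and any competing-event model can be left to the SAP.

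The cost is a wording change and one extra set of tables; no new data are needed. The drawback is that the added estimate includes time off drug, which is why the two should be shown together. The change concerns analysis only and does not touch patient management.
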